17 peginterferon alfa when added to long-term nucleoside therapy in patients with chronic HBV
18 infection (both HBeAg-positive and -negative). We hypothesize that the extended pretreatment with
19 NUCs will modify the responsiveness to peginterferon. These effects will be studied by analyzing the
20 expression pattern of ISGs, the response of NK cells prior to and after peginterferon injection
21 resulting in improved transcriptional control of cccDNA, the induction of antibodies against HBe and
22 HBsAg and T cell responses.

23 Primary endpoints of this trial will be the changes in expression levels of ISG's, intrahepatic total HBV
24 DNA and cccDNA content, changes in NK cell effector cell function measured before and following a
25 single dose of peginterferon stratified by treatment response and the rates of HBeAg and HBsAg loss
26 and seroconversion in HBeAg positive patients, HBsAg loss and seroconversion rate in HBeAg
27 negative patients. Secondary endpoints will be the induction of HBV-specific memory T cell
28 responses. A post-hoc analysis will stratify response rates upon available viral genotype data and
29 duration of NUC therapy prior to study enrollment. Other secondary end-points will include changes
30 in quantitative HBeAg and HBsAg levels during therapy and safety of the combination regimen.
31 Serological response rates, qHBsAg kinetics and safety end-points will be compared to historical
32 controls of published multicenter randomized trials comparing the efficacy of peginterferon and
33 NUCs in eAg positive and negative HBV carriers

34

HYPOTHESIS

In patients with chronic hepatitis B infection, under long-term viral suppression maintained by NUCs treatment, peginterferon add-on therapy will result in a greater proportion of subjects achieving serological response compared to before peginterferon was added. We hypothesize that response to treatment will be accompanied by measurable changes in host-response gene transcription profile, immune cell activation and function, and quantitative viral biomarker levels.

SPECIFIC AIMS

1. To assess the changes in ISG profile and NK cell function after a single dose of peginterferon in patients receiving long-term NUCs with maintained viral suppression
2. To determine rates of HBeAg and HBsAg loss with or without seroconversion and induction of HBV-specific memory T cells to peginterferon add-on treatment in eAg positive and negative HBV carriers on long-term NUC treatment.

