3. To identify pre- and on-treatment predictors of serological response to peginterferon add-on/nucleos(t)ide combination therapy.
4. To determine if there are differences in epigenetic regulation of cccDNA between HBeAg positive and negative CHB at baseline and following a single dose of peginterferon treatment

PROTOCOL OVERVIEW

We intend to enroll a total of 60 patients with HBeAg positive (n=30) and HBeAg negative (n=30) chronic HBV infection, who have been on-treatment with one or more nucleos(t)ide analogues for at least 192 weeks prior to study enrollment with maintained viral suppression (HBV DNA level <100 IU/ml). After a thorough medical evaluation and liver biopsy, participants will receive therapy with subcutaneous injections of peginterferon-alpha 2a at a dose of 180mcg per week for a total of 24 weeks. A second liver biopsy will be performed 6 hours following the first peginterferon injection for the purpose of assessing ISGs, intrahepatic NK cell quantity and function and intrahepatic viral biomarker response patterns. Most interferon induced genes achieve maximal response in the liver and periphery within 4 hours, begin to decline by 8 hours, and return to baseline levels by 24 hours post-administration of interferon. Because peginterferon is slower to be absorbed we have selected the six hour rather than a four hour time point.[38]

1 Patients will be followed carefully on weeks 0, 2, 4, 8, 12 and 24 during treatment and at 12 week
2 intervals thereafter until 48 weeks post-treatment.
3 During study visits patients will be assessed for compliance with study medications, as well as the
4 development of any treatment related side effects and/or adverse reactions. In addition, blood will
5 be drawn periodically for the assessment of routine blood tests, quantitative viral biomarker levels,
6 serological response markers and immune cell functional status.
7

8 **INCLUSION/EXCLUSION CRITERIA** 9

10 **Inclusion criteria: HBeAg positive group**

- 11
- 12 1) Age >18 years and older, male or female.
- 13 2) Known serum HBsAg and HBeAg positivity at the time of screening.
- 14 3) Ongoing treatment with one or more NUCs for at least 192 weeks before study entry.
15 Subjects may have a brief interruption of treatment for medical reasons (e.g. breast feeding)
16 not to exceed 8 weeks and none within the 48 weeks before study entry.
- 17 4) HBV DNA levels <100 IU/mL, measured at least 12 months prior to, and upon enrollment to
18 the study.

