14 and informed consent document; and (b) the characteristics of the subject population being studied.

15 2. Related or possibly related to participation in the research (possibly related means there
16 is a reasonable possibility that the incident, experience or outcome may have been caused by the
17 procedures involved in the research); and

18 3. Suggests that the research places subjects or others at a greater risk of harm (including
19 physical, psychological, economic or social harm) than was previously known or recognized).

20 Expected Adverse Events become unanticipated problems when they occur at a greater frequency or
21 severity than was previously known.

22
23 Adverse events, protocol deviations, unanticipated problems (UP), Unanticipated Adverse Device
24 Effects (UADEs), serious adverse events, sponsor and serious, are defined as described in NIH HRPP
25 SOP 16 ("Reporting Requirements for Unanticipated Problems, Adverse Events and Protocol
26 Deviations."). All adverse events at least possibly related to the patient's participation in the
27 research protocol, including those observed by or reported to the research team, will be recorded.
28 Serious unanticipated problems and serious protocol deviations will be reported to the IRB and CD
29 as soon as possible but not more than 7 days after the PI first learns of the event. Not serious
30 unanticipated problems will be reported to the IRB and CD as soon as possible but not more than 14
31 days after the PI first learns of the event.

32
33 Non-serious protocol deviations will only be reported to the IRB (within 14 days after the PI first
34 learns of the event) if they represent a departure from NIH policies for the conduct of human subjects
35 research, adversely affect the health care of the subject(s) or compromise the interpretation or
36 integrity of the research. Non-serious protocol deviations that result from normal subject scheduling

1 variations or technical issues associated with sampling that do not impact the health of the subject or
2 the interpretation of the study data will not be reported.

3

4 Adverse events that are expected as a part of treatment or procedures outlined in the protocol will
5 not be reported unless they occur at a rate or severity greater than known to occur in patients
6 undergoing the treatment or procedures. If AEs associated with the treatment and procedures in the

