7 study occur at a rate or severity greater than known to occur, they will be reclassified as a UP and
8 reported as such. AEs with known relation to the natural history of chronic hepatitis B or to other
9 pre-existing conditions will not be reported unless they occur at a rate or severity greater than
10 known to occur in patients with hepatitis B or the subject's other pre-existing conditions. AEs that
11 are unrelated to the research will not be reported. The PI is responsible for summarizing all
12 reportable serious adverse events and adverse events at least possibly related at the time of
13 Continuing Review. Deaths will be reported to the Clinical Director and IRB within 7 days after the PI
14 first learns of the event.

15

16

17

18

19 **PROTOCOL MONITORING PLAN**

20

21 Study procedures will be subject to audits and/or monitoring visits to ensure compliance
22 with the protocol and applicable regulatory requirements consistent with the Liver
23 Diseases Branch quality assurance program plan. Audit and/or monitoring visits results
24 will be reported to the Principal Investigator for further reporting as appropriate. Study
25 documents and pertinent hospital or clinical records will be reviewed to verify that the
26 conduct of the study is consistent with the protocol plan.

27

28 **ENROLLMENT OF CHILDREN, WOMEN AND MINORITY INDIVIDUALS**

29

30 The current protocol excludes children (age limit > 18 years) as the Liver Diseases Branch does not
31 currently treat children. The number of children on long-term nucleos(t)ide analogue therapy would
32 expected to be small and the requirement for two liver biopsies may be prohibitive.

1 Chronic HBV infection is about twice as common among men than women. We expect to include
2 women in the proportions that occur in this disease. Thus, we expect 30% to 40% of patients to be
3 women. The exclusion of women interested in getting pregnant or who are not able to practice
4 adequate birth control would be the only possible bias introduced in attaining adequate
5 representation of women in this study.

6 The distribution of minority individuals in our ongoing hepatitis B study (07-DK-0207) are as
7 follows: 73% of subjects were considered minorities, 82% of whom were Asian and 14% African-
8 American based on self-reported race and ethnicity and NIH, HHS guidelines for defining minority
9 race. Thus, we believe minority individuals will be adequately represented in this study.

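### The adverse-event recording rule requires only events judged at least possibly related, so clinical event rates may be understated in the planned comparison with published trials

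*Combined protocol and SAP*

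**What the plan says.** The recording rule is in the protocol section Adverse Event Reporting. It covers "All adverse events at least possibly related to the patient's participation in the" and continues "research protocol, including those observed by or reported to the research team, will be recorded". No other section requires unrelated events to be recorded. The Protocol Overview likewise describes visit assessment in terms of treatment-related effects and reactions.

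The same section then restricts reporting. Events that "are unrelated to the research will not be reported". The category "AEs with known relation to the natural history of chronic hepatitis B or to other" pre-existing conditions is exempt unless the rate or severity exceeds what is known. Expected events of treatment or procedures are held to the same test.

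The last endpoint paragraph of the Background lists safety of the combination regimen as a secondary end-point and states: "Serological response rates, qHBsAg kinetics and safety end-points will be compared to historical" "controls of published multicenter randomized trials comparing the efficacy of peginterferon and" NUCs. The numbered list under Secondary endpoints does not contain safety, and Statistical Analysis has no safety analysis. Nothing withdraws the Background statement.

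**The concern.** A comparison of event rates between a single-arm trial and published trials is fair only if both sides count the same thing. Here the count depends on a causality judgement made by the investigators of an open study, and the plan does not match that count to the comparators' counting rule.

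The NUC is the sharpest case. Patients have taken it for at least 192 weeks before entry and continue it throughout. The section's explanation of possible relatedness, given under the definition of an unanticipated problem, refers to causation by procedures of the research. A clinical event blamed on the long-standing NUC can therefore be judged unrelated to participation and left out, although it belongs to the safety of the combination.

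The loss would be permanent. Analysis methodology promises a fuller analysis plan before data analysis, but no later plan can restore clinical events that were never written down. The check on whether known events exceed their known rate would use the same filtered count.

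**Working it through.** **The plan's own figure.** The documents give no safety figure to reproduce. Their one sample-size calculation concerns efficacy. Assuming two-sided alpha 0.05, n = (1.960 + 0.842)² × p1(1 − p1)/(p1 − p0)² gives 7.85 × 0.2275/0.0625 = 28.6, so 29, and 7.85 × 0.21/0.0625 = 26.4, so 27. Both match Power calculation, and neither bears on this point.

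**What is collected with and without a causality filter.**
- Filtered: clinical adverse events, by the recording rule.
- Not filtered: Chemistry 20 (including ALT and creatinine), CBC, the symptom questionnaire and the visual analogue scale at every visit in Table 1, and the fatigue scale at selected visits. Appendix 1 grades ALT by multiples of the upper limit of normal, so relatedness does not enter.
- Ambiguous: Monitoring schedules adverse-event review at the outpatient treatment visits and at week 24 without stating a filter, but does not say that unrelated events are to be recorded.

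The question is therefore confined to clinical adverse events.

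**Size if the comparators counted all events.** Let p be the true rate in both this trial and the comparator, and u the share of affected patients whose events are all judged unrelated. The documents give neither.

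Recorded rate = p(1 − u); shortfall = p × u.

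At p = 20%:
- u = 25%: 20% × 0.75 = 15%, a shortfall of 5 points (9 of 60 patients instead of 12).
- u = 50%: 20% × 0.50 = 10%, a shortfall of 10 points (6 of 60 instead of 12).

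For a commoner end-point, such as any adverse event, take p = 70%, n = 60, a fixed comparator rate and an exact binomial lower-tail test at 0.025. The test is an assumption, since the plan names none.

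| u | Recorded rate | Shortfall | Chance of falsely finding this trial safer |
|---|---|---|---|
| 0% | 70% | 0 | 2% |
| 5% | 66.5% | 3.5 points | 7% |
| 10% | 63% | 7 points | 19% |
| 20% | 56% | 14 points | 59% |
| 30% | 49% | 21 points | 91% |

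Over p = 50% to 90% and u = 5% to 30%, the shortfall runs from 2.5 to 27 points and the false-finding chance from 3% to over 99%.

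**Size if the comparators counted related events only.** Both sides then use the same filter, and the shortfall from this source is about zero. Setting all-cause events here against related-only events there would reverse the error, overstating this trial's rate by p × u.

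**With every event recorded and compared like with like.** In the all-cause comparison u = 0, the shortfall is zero, and the false-finding chance is 1.4% to 2.0% over the same range of p, within the nominal 2.5%.

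**The case against.** The case against has real weight, and most of it narrows the point.

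- The rule says what will be recorded and does not forbid recording more. The explicit exclusions concern reporting to the IRB and Clinical Director. This stands: a reader might infer that unrelated events are barred from the record, and the text does not say so. But nothing asks for them either, so a site that follows the rule exactly can omit them.
- A reader might infer that the trial will look safer than its comparators. That requires the published trials to have counted events regardless of cause, which the documents do not state. Only *may* is supportable.
- A reader might extend the point to ALT flares, for which Hazards and Discomforts quotes 12% and 18% above 10 × ULN. That fails. ALT is drawn on schedule whatever the cause, and the section notes that those figures come from patients not on oral antivirals.
- The direction is not certain overall. Events from the two study biopsies count as related to participation, and local pain is quoted at about 20% of percutaneous biopsies. If the comparators had fewer biopsies (not stated), this pushes the other way.
- The threshold for possible relatedness is low, so u may be small. The 25% to 50% range is illustrative only.
- A reader might take the rate check as the only study-level safety signal. Data and Safety Monitoring also provides weekly review of all study patients and monitoring by the statistical department, and deaths are reported without a relatedness condition.
- The comparison is a single Background sentence. This limits the weight of the point, but the comparison is still planned.

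**Conclusion.** The concern holds in limited form. The recording requirement stops at events judged at least possibly related to participation, a comparison of safety end-points with published trials is planned, and nothing aligns the two. Clinical adverse-event rates may be understated by p × u if the comparators counted events regardless of cause, for example 15% to 10% recorded against a true 20% when u is 25% to 50%. The bias from this source is about zero if they counted related events only. Both p and u are assumptions, and the comparators' rule is unknown. The documents do not support a claim that the trial is certain to look safer, or that laboratory or questionnaire end-points are biased. Action is still warranted under either comparator rule: a full record with relatedness fields permits both comparisons, whereas the present rule guarantees only the related-event one.

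**What to change.** Amend the recording sentence in Adverse Event Reporting so that all clinical adverse events are recorded regardless of cause, graded with Appendix 1, with separate relatedness fields for peginterferon, the NUC and biopsy. Define the safety end-points. For each historical source, establish how it counted events and compare like with like: all-cause with all-cause, related with related. Do not prescribe all-cause counts for every comparison. Apply the same matching to the check on whether events exceed their known rate. Keep the relatedness filter for IRB reporting only.

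The cost is protocol wording and somewhat more data entry for 60 patients, who already have adverse-event review at every visit in the first row of Table 1. Reported event rates will be higher. No treatment rule changes.

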23 peginterferon-alpha 2a (PEGASYS®, Roche), 180 mcg per week administered by subcutaneous
24 injection for a total of 24 weeks. Patients will continue treatment with their previous nucleosi(t)ide
25 analogue regimen during the treatment and follow-up phases of this study.

26 Patients will be seen in the outpatient clinic at weeks 2, 4, 8, 12, and 24, during treatment phase, at
27 12 week intervals thereafter up to 48 weeks post-therapy

28 Compliance will be monitored by medication diaries and counting of the residual vials returned at
29 outpatient visits. The side effects will be monitored regularly at each visit during the treatment phase
30 of the study by symptom questionnaires. Peginterferon alfa-2a will be dose reduced or stopped per
31 the dose reduction and stopping rules for peginterferon alfa-2a. Peginterferon alfa-2a treatment can
32 be restarted if the adverse event resolves and the patient is willing to re-start the medication.

33

34 **On-treatment liver biopsy**

35

1 At day 0, all patients will be readmitted to the NIH Clinical Center to start therapy with peginterferon
2 alfa-2a and to undergo a repeat liver biopsy. Biopsy will be scheduled at 6 hours following the first
3 injection of peginterferon, for the purpose of assessing ISG response pattern following the initial
4 exposure to peginterferon. Liver tissue will also be subjected to routine histopathological grading
5 and staging as well as for immune cell, quantitative viral kinetic and cccDNA epigenetic studies as
6 previously described.

7
8 Since the hypothesis to be tested in this study is that response to treatment peginterferon (i.e. loss of
9 HBeAg and HBsAg or both) is mediated by changes in hepatocyte gene transcription profile, it is
10 necessary to obtain liver tissue at two time points-before and 6 hours after the first dose of
11 interferon. Performing two liver biopsies within 12 weeks or even as short as 24 hours has been
12 performed in other Liver Disease Branch studies and has not been associated with an increase in the
13 complication rate or lower patient acceptance.

16 **Monitoring**

17 Day 0

- 18
- 19
- 20 1) Brief clinical evaluation
- 21 2) Review patient's eligibility for study
- 22 3) Symptom questionnaire
- 23 4) Visual analogue scale
- 24 5) Fatigue questionnaire (Promise 7)
- 25 6) Chemistry 20 (sodium, chloride, potassium, bicarbonate, calcium, phosphate, magnesium,

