6 predictive factors associated with a favorable response to peginterferon therapy when added on to
7 long-term NUCs treatment, in patients with HBeAg positive and negative chronic HBV infection.

8

9 **Primary end-points**

10

- 11 1) The primary end-point for this study will be the change in level of ISG expression and NK cell
12 responses before and after 1st peginterferon injection in responders versus non-responders
13 to peginterferon add-on therapy.
- 14 2) Proportion of eAg positive patients showing eAg loss with or without seroconversion at end
15 of treatment and 24 and 48 weeks off therapy.
- 16 3) Proportion of eAg positive patients showing sAg loss with or without seroconversion at end
17 of treatment and 24 and 48 weeks off therapy
- 18 4) Proportion of eAg negative patients showing sAg loss with or without seroconversion at at
19 end of treatment and 24 and 48 weeks off therapy

20

21 **Secondary endpoints**

22

- 23 1. Level of qHBsAg decline at treatment week 12, at end of treatment and 24 and 48 weeks off
24 therapy, compared to pretreatment levels in eAg positive and negative patients
- 25 2. Level of qHBeAg decline at treatment week 12, at end of treatment and 24 and 48 weeks off
26 therapy, compared to pretreatment levels in eAg positive and negative patients
- 27 3. Correlation of qHBsAg levels at initial evaluation, week 12,24,36 and 48 with intrahepatic
28 pregenomic and cccDNA concentration before and after initiation of peginterferon in
29 responders versus non-responders to treatment.
- 30 4. Intrahepatic pregenomic and cccDNA concentration before and after starting treatment with
31 peginterferon.
- 32 5. Epigenetic alterations in HBeAg positive and negative patients following first 1st
33 peginterferon injection compared to pretreatment levels as measured by chromatin
34 immunoprecipitation (ChIp) assays

- 1 6. Frequency and functional activity of circulating and liver infiltrating, HBV-specific T-cells,
2 measured before and during treatment in responders versus non-responders to
3 peginterferon add-on therapy.
4

5 DOSE CHANGES 6

7 **Stopping peginterferon therapy:** 8

9 Add-on peginterferon will be discontinued early for any of the following reasons:

- 10 a) **Toxicity**- the dose of peginterferon will be modified or discontinued according to Table 1:
11 Peg-Interferon Alfa-2a Dose Modification Guidelines (see below).
12 b) **Withdrawal of informed consent** (subject's decision to withdraw for any reason.

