It is not possible to calculate power for the primary endpoints. We have calculated power for the secondary endpoints of the rates of HBeAg and HBsAg loss. Response rates in patients in both groups will be compared to historical controls of HBeAg positive and negative. It is assumed that if these patients were followed for an additional year without peginterferon, only 10% of the HBeAg positive patients would become HBeAg negative and 5% of the HBeAg negative patients would become HBsAg negative. A sample size of 29 HBeAg positive and 27 HBeAg negative patients will provide the study with a statistical power of 80% to detect a difference of 25% (35% versus 10% for HBeAg loss and 30% versus 5% for HBsAg loss). The sample size was increased to 30 patients in each arm to allow for withdrawals.

Variables to be analyzed in association with a serological response will include: baseline ALT and HBV DNA level, liver histology, HBV genotype, IL28B genotype, duration of NUC therapy, and ISG levels. Patients with missing data or who drop out of the study will be considered as treatment failures on an intention to treat basis. For comparison of means, Student's t-test will be used. All reported p-values will be 2-sided.

Demographics and Baseline Characteristics

The following will be summarized for treated subjects:

- Demographics: age, race, gender, geographic region, ethnicity;
- Disease characteristics at baseline: HBV DNA level, HBV genotype, IL28B SNP genotype and cirrhosis status, duration of NUC therapy;
- Physical measurements at baseline; height, weight, body mass index, hip and waist circumference;
- Laboratory tests at baseline;

Analysis plan

To address the primary hypothesis that ISG levels are related to virological response to peginterferon, the ISG analysis of the on treatment liver biopsy at 6 hours after the first dose of interferon will be correlated with off-peginterferon serological outcome (HBeAg loss/seroconversion and HBsAg loss). To address the hypothesis that ISG levels are related to HBsAg levels, the ISG analysis of the on treatment liver biopsy will be correlated with HBsAg levels at weeks 4, 12, 24.. The

1 analyses will be stratified by HBV genotype and duration of NUC therapy.

2

3 **Analysis methodology**

4

5 The analysis will be based on standard approaches to analysis of microarray data. Since the software
6 and approaches change frequently in this field, we will provide a broad outline of the approach

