34 their potential eligibility. Subjects will discuss protocol eligibility with the principal investigator or
35 an associate investigator, and associate investigators will continue to be involved in research
36 activities throughout subjects' participation in this study. Information collected about subjects will be
obtained through routine clinical interactions including documentation in the subjects' medical

1 charts and through questionnaire completion, patient diaries and telephone calls. We will verbally
2 verify with subjects their partner's compliance with subject reported reproductive contraception use,
3 but this information will not be documented in the subjects' medical charts as these individuals are
4 not considered subjects under this study. The information collected from subjects is primarily
5 required to manage the subjects' clinical care under the current study. Data collected for research
6 only is the minimal information required to complete analysis for primary and secondary aims.
7
8

9 **CONSENT PROCESS**

10
11 Potential study subjects will be informed of study rationale, design, participation burden, risks,
12 benefits and side effects of therapy during routine LDB clinic visits and will have an opportunity to
13 ask questions about the proposed study. They will be provided a copy of the study consent form to
14 take home and review in more detail. . Consent will be obtained by the Principal Investigator, or an
15 Associate Investigator following the subject's review of the provided consent documentation during a
16 subsequent clinic visit. If a subject indicates a desire to participate in the research study, he/she will
17 have all screening laboratories, radiologic imaging and if necessary, liver biopsy, performed through
18 this protocol. The initial liver and second liver biopsy for participation in this study will be for
19 research purposes. Patients who refuse either liver biopsy will be excluded from further
20 participation in the study, since one of the primary endpoints of the trial is based on analysis of
21 change in ISG levels comparing the second to the first liver biopsy. Potential study subjects who meet
22 study inclusion and exclusion criteria will sign the consent form to participate in this study during a
23 scheduled LDB clinic visit prior to screening.
24

25 We do not plan to enroll non-English speaking subjects; however they are not excluded from

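### Read literally, a patient who refuses the second biopsy after the first peginterferon injection leaves the study and counts as a serological failure, although the serological end-points need no biopsy

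*Combined protocol and SAP*

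**What the plan says.** - **Refusal.** Consent Process: "Patients who refuse either liver biopsy will be excluded from further" "participation in the study, since one of the primary endpoints of the trial is based on analysis of" the change in ISG levels between the two biopsies. The rule covers either biopsy and draws no line at the first dose.
- **Timing.** On-treatment liver biopsy: patients are readmitted on day 0 to start peginterferon and be re-biopsied. "Biopsy will be scheduled at 6 hours following the first" injection.
- **Missing data.** Statistical Analysis, Power calculation: "Patients with missing data or who drop out of the study will be considered as treatment failures on an intention to treat basis".
- **End-points that need no tissue.** Primary end-points 2 to 4 are serological. Number 2 is "Proportion of eAg positive patients showing eAg loss with or without seroconversion at end" of treatment and at 24 and 48 weeks off therapy; number 3 is HBsAg loss in the same group; number 4 is "Proportion of eAg negative patients showing sAg loss with or without seroconversion at at" the same times. The NK samples at 6 and 24 hours after the injection (Monitoring, Day 0 and Day 1) are also blood draws.
- **Stopping the drug.** Stopping peginterferon therapy: "Add-on peginterferon will be discontinued early for any of the following reasons", followed by items a) to e). Refusal of a biopsy is not among them. Continued follow-up is written out there for pregnancy only.

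**The concern.** The reason given for the exclusion concerns one end-point, but the exclusion is from the whole study. For a patient who has had the injection and then declines the biopsy, the tissue comparison is lost whatever the rule says. The planned safety visits, the serology to post-treatment week 48 and the blood NK samples could still be obtained. Ending participation gives them up without need.

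Two things are at stake. The first is scheduled safety observation of someone who has just received a long-acting interferon. The second is completeness of the single-arm response rates that are to be compared with historical rates: each such patient puts 1 of 30 in a group (3.3 percentage points) into the failure category whatever the true outcome. The error goes one way, lowering the observed rate. The comparison of liver ISG change between responders and non-responders is not affected, because these patients have no paired tissue.

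**Working it through.** **Inputs.** From Power calculation: HBeAg loss 35% against 10%; HBsAg loss 30% against 5%; 80% power; 29 and 27 patients, raised to 30 per group for withdrawals; two-sided p-values. Assumed, because the plan does not state them: alpha of 5%, the test, and the number *k* of dosed refusers in a group.

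**Step 1: the plan's own sample size.** A one-sample normal formula with the variance at the alternative, n = (1.960 + 0.842)² × p1(1 − p1)/(p1 − p0)², reproduces both figures:
- HBeAg loss: 7.849 × 0.35 × 0.65/0.25² = 28.57, so 29.
- HBsAg loss: 7.849 × 0.30 × 0.70/0.25² = 26.37, so 27.

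The allowance for all withdrawals is therefore 1 of 30 in the HBeAg-positive group and 3 of 30 in the HBeAg-negative group.

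**Step 2: an exact test.** Take the smallest count with upper-tail probability at most 0.025 under the historical rate. This is 8 of 30 for HBeAg loss (tail 0.0078) and 5 of 30 for HBsAg loss (tail 0.0156).

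**Step 3: *k* refusers scored as failures.** Expected observed rate = p1 × (30 − k)/30. Exact power for HBeAg loss = P(X ≥ 8 | n = 30 − k, p = 0.35), and for HBsAg loss = P(X ≥ 5 | n = 30 − k, p = 0.30).

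**Step 4: *k* refusers followed, observed result counted.** Exact power for HBeAg loss = Σj P(J = j | k, q) × P(X ≥ 8 − j | n = 30 − k, p = 0.35), where q is the refusers' own response rate. Two values bracket it: 10%, the plan's rate for another year without peginterferon, and 35%, its rate for the full course.

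| k of 30 | HBeAg loss: expected rate if scored failures | power if scored failures | power if observed, q = 10% | power if observed, q = 35% | HBsAg loss: power if scored failures |
|---|---|---|---|---|---|
| 0 | 35.0% | 87.6% | 87.6% | 87.6% | 97.0% |
| 1 | 33.8% | 84.9% | 85.7% | 87.6% | 96.2% |
| 2 | 32.7% | 81.8% | 83.5% | 87.6% | 95.3% |
| 3 | 31.5% | 78.2% | 81.2% | 87.6% | 94.1% |

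The part due to failure scoring is the difference from the matching observed column. At q = 10% it is 84.9 to 85.7, 81.8 to 83.5 and 78.2 to 81.2, or 0.8, 1.7 and 3.0 points. At q = 35% it is 2.7, 5.8 and 9.4 points.

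**Step 5: the same question by the Step 1 formula.** With the reduced rate p from Step 3, power = Φ[(p − p0)√30/√(p(1 − p)) − 1.960]. For k = 0, 1, 2, 3 this gives 81.9%, 78.8%, 75.4% and 71.7% for HBeAg loss, and 84.8%, 82.6%, 80.1% and 77.5% for HBsAg loss. On that scale one forced failure takes the HBeAg-positive group below 80%, and three take the HBeAg-negative group below it.

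**The case against.** The rule sits in the consent section, and its ordinary purpose is a condition of entry: accept both biopsies or do not take part. To reach a dosed patient, someone must complete the first biopsy, return for the day-0 admission, accept the injection and then refuse within 6 hours. The On-treatment liver biopsy section reports no lower acceptance of closely spaced biopsies in the group's other studies, so there may be no such patient. Counting an early withdrawal as a failure is also a conventional, conservative choice. All of this stands, and it limits the size of the point.

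Three stronger readings are tempting, and the documents do not support them:

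- *Refusers in general have been dosed.* Only those who refuse between injection and biopsy have been. A refusal before the injection leaves the patient undosed.
- *The plan states that follow-up ends and that refusers are failures.* It states neither. Both follow from reading the exclusion rule and the missing-data rule together. Adverse Event Reporting requires that adverse events at least possibly related to participation be recorded when observed by or reported to the team, and most patients are expected from the branch's own clinic, so contact need not be lost. That provision does not supply scheduled visits or serology.
- *A patient who refuses the first biopsy is scored as a peginterferon failure.* This is weak. The groups of 30 are formed after the pretreatment biopsy to receive the drug, and baseline summaries are for treated subjects.

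It is also fair to say that the full fall in power cannot be charged to the scoring rule. If peginterferon stops after one dose, much of the loss comes from stopping treatment, as the 10% column shows.

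**Conclusion.** The point holds for a narrow case. The exclusion rule, the 6-hour timing and the missing-data rule, taken as written, remove a dosed patient who refuses the second biopsy from scheduled follow-up and count that patient as a failure on end-points that need no second biopsy. No section provides otherwise.

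The size is modest and conditional. With 1 to 3 such patients of 30, failure scoring costs about 1 to 3 points of exact power for HBeAg loss if they would respond at 10%, and about 3 to 9 points if at 35%. For HBsAg loss in HBeAg-negative patients exact power stays at 94% or more. These figures rest on an assumed two-sided 5% level, an assumed exact test and an assumed number of refusals. The normal formula that matches the plan's sample sizes gives lower levels and steeper falls. The change is still worth making, because it is cheap and it also secures safety observation after a dose.

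**What to change.** Amend the Consent Process rule so that refusal of the second biopsy after the first peginterferon dose removes the patient only from the paired-liver-tissue analyses. The already scheduled safety, serology and blood NK assessments then continue with the patient's agreement, and the observed serological result is counted. Add one sentence to the Analysis plan defining the serological denominator as patients who received at least one dose of peginterferon. That also settles the status of anyone who refuses before dosing.

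Whether peginterferon itself continues in such a patient is a separate matter. The sponsor must reconcile the Consent Process rule with the list under Stopping peginterferon therapy and state the answer.

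The cost is a short amendment and one analysis-set sentence. The downside is that a few patients may complete planned visits without contributing paired liver tissue.
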